5.3 Identification

ACell Gentrax Surgical Matrix PSM will be provided as product number PSM0412 which comes in one-time use 4 x 12cm strips.

5.4 Packaging and Labeling

ACell Inc. will provide the Gentrax PSM. Gentrax PSM is supplied E-Beam terminally sterilized in a double Tyvek pouch configuration all contained within an external box. Gentrax PSM will be provided as product number PSM0412 which comes in 4 x 12cm strips. Each subject will have one device implanted.

5.5 Storage, Handling, Disposal and Dispensing

Storage

Gentrax PSM is to be stored in a clean, dry environment at ambient temperature approximately 25°C (77°F) in unused and undamaged packages.

Handling and Disposal

The Gentrax PSM will be handled according to standard aseptic/sterile techniques.

Dispensing

The Gentrax PSM will be removed from the packaging according to standard aseptic/sterile technique. The material will be rehydrated in a sterile dish by submerging completely in room temperature sterile saline or sterile lactated Ringer's solution. The minimum rehydration time for Gentrax PSM is 15 minutes.

5.6 Initial Orders

MSK will maintain a minimum par level of two (2) Gentrax PSM devices and a maximum par level of eight (8) on the shelf at all times.

MDACC will maintain their own supply in accordance to their own independent contract with ACell

5.7 Re-Supply

Upon depletion of par levels to the minimum required quantity of two Gentrax PSM devices, MSK will re-order through standard MSK procedures. All products will be directly shipped by ACell to MSK under standard ACell shipping procedures.

6.1 CRITERIA FOR SUBJECT ELIGIBILITY

Describe the characteristics of the patient/subject population.

6.2 Subject Inclusion Criteria

- Patient 18 years of age or older
- Pathologically confirmed Gastric, Gastroesophageal Junction (GEJ) or Esophageal, adenocarcinoma at either MSKCC or a participating site (biopsy may be performed at other institutions but slides must be confirmed at MSKCC or a participating site, as is routine care at our institution)
- Patient undergoing any resection requiring an anastomosis to the esophagus for curative intent. Including but not limited to esophagectomy or total gastrectomy.
- Subject is willing to provide written informed consent

- Subject is willing and able to comply with the follow-up regimen

6.3 Subject Exclusion Criteria

- Pregnant or lactating women
- Intraoperative evidence of metastatic or locally-unresectable disease
- Patients with known sensitivity or allergy to porcine materials.
- Patients undergoing any resection requiring an anastomosis to the esophagus for palliative intent.

7.0 RECRUITMENT PLAN

Patients from MSKCC will be recruited from the GMT and Thoracic surgical clinics at [name], [name] GMT surgical clinic at Basking Ridge and [name] clinic at West Harrison. Two thirds of all patients (approximately 57) will come from the GMT clinics and one third of all patients (approximately 29) will come from the Thoracic clinics. Patients will also be enrolled at MDACC.

In most cases, the initial contact with the prospective subject will be conducted either by the treatment team, investigator or the research staff working in consultation with the treatment team. The recruitment process outlined presents no more than minimal risk to the privacy of the patients who are screened and minimal PHI will be maintained as part of a screening log. For these reasons, we seek a (partial) limited waiver of authorization for the purposes of (1) reviewing medical records to identify potential research subjects and obtain information relevant to the enrollment process; (2) conversing with patients regarding possible enrollment; (3) handling of PHI contained within those records and provided by the potential subjects; and (4) maintaining information in a screening log of patients approached (if applicable).

This screening log of identifiable patient information will be kept in a password protected MSKCC registered database, CAISIS.

8.1 PRETREATMENT EVALUATION

- Signed Written Informed Consent
- Patients must be surgical candidates for esophageal anastomosis via TG, PG or Esophagectomy
- Relevant/Interval Medical History
- Physical examination
- Baseline Toxicity Evaluation
- Pre-Surgical Testing per Standard of Care of the site of device implementation.

9.1 TREATMENT/INTERVENTION PLAN

[figure not shown]
9.2 Management common to both groups

There are no restrictions on preoperative antibiotics, approach (laparoscopic or open), incision, and extent of lymph node dissection, margins, or other features of the

resection: the surgeon should proceed as he or she normally would in the absence of the trial. Most surgeons at MSKCC perform stapled gastrointestinal anastomoses but the type of primary anastomosis performed (stapled or hand-sewn) would be left to the discretion of the surgeon. Similarly, surgeons have the discretion to use nasogastric tubes or drains if they desire. Patients would undergo standard oncologic resection of their tumor by esophagectomy, PG or TG depending on site of disease. Patients with clinical evidence of advanced disease may undergo an initial laparoscopy procedure to evaluate for metastases prior to resection. Patients found to have metastatic disease would not undergo resection and would not be eligible for the study. Up to this point in the treatment course, all procedures would have been routine.

9.3 Anastomotic reinforcement with ACell Gentrix PSM

All esophageal anastomoses will be reinforced circumferentially with ACell Gentrix PSM. The material will be secured with ~ 2 cm overlap of the material proximal and distal to the anastomosis (see below).

ACell Gentrix PSM shown wrapped circumferentially around an esophagojejunal anastomosis with anchoring stitch after total gastrectomy reconstruction.

After anastomotic reinforcement, the procedure will be completed in a routine fashion with final assessments for hemostasis, drain placement when indicated, and wound closure.

9.4 Postoperative care

Most inpatient postoperative management decisions will be left to the discretion of the surgeon, including intravenous hydration, removal of nasogastric tubes or drains, initiation of diet, investigations, management of complications, and discharge. Post-operative length of stay will be as per routine of the surgeon. All patients undergoing esophagogastric resection will have a contrast swallow evaluation on post-operative day #4-10 to assess for radiographic evidence of anastomotic leak.

Outpatient management will entail postoperative follow up visits at 21 days (+/- 7 days), and at 90 days (+/- 14 days). If during the follow up period, patients report any symptoms suggestive of anastomotic stricture, a contrast study (esophagram) or endoscopy will be obtained at that time to evaluate for stricture. These tests will be performed as per standard postoperative assessment by the surgeon.

10.1 EVALUATION DURING TREATMENT/INTERVENTION

Clinical assessment for anastomotic leak will be carried out during the course of the hospitalization after surgery and up to 90 days +/- 14 days postoperatively. One radiographic assessment for leak will be performed during the interval from postoperative day 4-10. The grade of leak will be assigned according to standard criteria. For patients who die in the first 120 days following surgery where no documentation of leak has occurred, a request for autopsy will be made to determine the cause of death and will clarify whether or not a leak had occurred.

Clinical assessment for stricture will take place at 90 days +/- 14 days postoperatively. Patients will be evaluated in the outpatient clinic and will be assigned a dysphagia score from 0-4 by the RSA or clinical staff based on the following scale:

- 0 – Able to eat a normal diet
- 1 – Able to eat some solid food
- 2 – Able to eat semisolids only
- 3 – Able to swallow liquids only
- 4 – Unable to swallow anything

A dysphagia score of ≥ 2 will prompt further work up with upper endoscopy and possible dilatation if stricture is identified.

Patients may also be called by a member of the research team check on their health status until the study closes. This will allow for more robust data to be collected on the long term affects of the Gentrix implantation.

Data for cost metrics will be collected postoperatively through POD90 (+/- 14 days). These include metrics such as Length of Stay, Readmission, Complications, Reoperation and Total Hospital Bill. Total hospital bill data will be obtained from the Physician Billing Department. Data will be collected for all 86 patients enrolled and summarized. Cost of total hospital bill will be determined from the date of admission on protocol to day of discharge on protocol. Additional cost of re-admission to day of discharge of re-admission will so be included.

Examination/Intervention	Preop Visit(s)	OR	POD 4-10	POD21 (+/- 7 days)	POD90 (+/- 14 days)	Every 3 months until the study closes
Obtain Informed Consent	X					
Relevant / Interim Medical History	X			X	X	
Physical Exam	X					
Pre Surgical Testing	X					
Surgery		X				
Implantation of Gentrix PSM		X				
Thin-barium or Gastrografin Swallow Evaluation			X			

Dysphagia Score				X	
Symptom Assessment			X	X	
AE Assessment	X		X	X	
Review of the patient's medical record					X

*Note: A member of the research team may contact the patient via telephone until the study closes.

This phone call will assess the patient's well being after surgery.

Table 10.1 – Assessments and investigations during the course of the trial. An “X” denotes an assessment or test that all patients will undergo.

11.0 TOXICITIES/SIDE EFFECTS

Esophagectomy, PG and TG are substantial operations with associated morbidity including anastomotic leak, stricture, and bleeding. All patients undergoing esophagectomy, PG or TG are at risk of these events irrespective of entry into the trial. The most common complications include anastomotic leak, bleeding, wound infection, anastomotic stricture, and bowel obstruction. We do not anticipate increased toxicity or side effects as a result of anastomotic reinforcement with Gentrix PSM. However we will carefully evaluate for and document any potential adverse events such as infection, chronic inflammation, fistula formation, seroma formation, hematoma, recurrence of tissue defect, allergic reaction, and fever or chills as is our standard protocol.

Postoperative toxicities will be graded on a scale of 0 to 5 as described by the NCI-Common Terminology for Adverse Events (CTCAE) version 4.0.

12.0 CRITERIA FOR THERAPEUTIC RESPONSE/OUTCOME ASSESSMENT

The primary outcome of the trial is the rate of anastomotic leak after reinforcement of esophageal anastomoses with Gentrix PSM. Esophageal anastomotic leaks will be determined by one routine postoperative contrast swallow study on 4-10 as well as clinical course. Anastomotic stricture formation occurs later in the postoperative period and will be diagnosed based on symptomatology. Patients reporting symptoms consistent with stricture will be evaluated with radiographic contrast swallow study or endoscopy.

13.0 CRITERIA FOR REMOVAL FROM STUDY

The intervention in this trial is an isolated event (surgery), with routine post-operative care. Thus, there are no criteria to remove patients from the trial other than patient withdrawal of consent or death. Patients are permitted to withdraw consent at any time if they desire and will not undergo further trial investigations if they do so. Patients will be made aware that they cannot have the Gentrix PSM removed once it is implanted.

14.0 BIOSTATISTICS

The historical control leak rate at our institution among patients receiving partial, total gastrectomy or esophagectomy is 8-15%: esophagectomy leak rate of around 15% and total and proximal gastrectomy leak rate of around 10%. A weighted average of 13% between the groups will be considered an unacceptable leak rate. We will employ Simon's two stage design to show a decrease in the leak rate assessed radiographically and clinically from 13% to 5% which would require 86 total patients to detect this difference with type I and II error rates of 10% each. In the first stage we will enroll 43 patients and if 5 patients experience a leak, then the study will be terminated, however if only 4 or less patients experience a leak then we will proceed to accruing up to 86 patients. If at the end of the second stage we see 7 or less leaks then we will consider the study worthy of further investigation. We expect two thirds of the accrued patients to have total gastrectomy performed while the rest to receive esophagectomy. Exact 95% confidence intervals will be computed for the leak rate for all the patients as well as separately for esophagectomy and total gastrectomy.

Similarly, the stricture rate will be estimated using binomial proportions and exact 95% CI will be computed.

The different cost metrics will be summarized descriptively: continuous cost metrics will be summarized using medians and ranges while binary variables will be summarized using binomial proportions.

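### The 13% null leak rate does not match the planned case mix, which averages 11.7%; at that rate a device with no effect passes about 17% of the time, not 10%

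*Combined protocol and SAP*

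**What the plan says.** All the inputs to the primary decision rule are in Section 14.0.

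- Historical rates, in per cent: "esophagectomy leak rate of around 15% and total and proximal gastrectomy leak rate of around 10".
- Null rate: "A weighted average of 13% between the groups will be considered an unacceptable leak rate". The weights are not given.
- Planned mix: "We expect two thirds of the accrued patients to have total gastrectomy performed while the rest to receive esophagectomy". Section 7.0 (Recruitment Plan) gives a matching split by clinic: "Two thirds of all patients (approximately 57) will come from the GMT clinics", with the remaining 29 or so from the Thoracic clinics.
- Target and error rates: the aim is "to show a decrease in the leak rate assessed radiographically and clinically from 13% to 5" per cent, which "would require 86 total patients to detect this difference with type I and II error rates of 10% each".
- Stage 1: "In the first stage we will enroll 43 patients and if 5 patients experience a leak, then the study will be terminated"; with 4 or fewer leaks accrual goes on to 86.
- Final rule: 7 or fewer leaks among the 86 makes the approach worth further study.

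**The concern.** A weighted average of 10% and 15% with two thirds of the weight on the 10% group must lie nearer 10% than 15%. The stated 13% lies nearer 15%, so the null rate and the planned mix in the same paragraph cannot both be right.

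This matters because the trial has one arm and no randomization (Section 15.3), so the historical rate is the only comparator. The primary objective in Section 2.1 is to find out whether reinforcement lowers the leak rate. The null therefore has to be the rate these patients would have if the device did nothing. If the null is set above that rate, the trial can pass because it enrolled mostly lower-risk gastrectomy patients, and the 10% type I error does not hold for the patients it plans to enrol.

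**Working it through.** **Inputs (Section 14.0).** Esophagectomy rate 15%; gastrectomy rate 10%; mix 1/3 and 2/3; p0 = 13%; p1 = 5%; n1 = 43, continue at 4 or fewer leaks; N = 86, success at 7 or fewer. The clinic split of 57 and 29 is from Section 7.0.

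**Step 1: reproduce the stated design.** With leak probability p in every patient,

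P(pass | p) = Σ (x = 0 to 4) P(X1 = x) · P(X2 ≤ 7 − x), where X1 and X2 are independent Binomial(43, p).

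- p = 13%: P(pass) = 0.0989, the type I error.
- p = 5%: P(pass) = 0.9012, the power.

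Both agree with the stated 10% error rates. In a search over two-stage designs for 13% against 5%, this one also had the smallest expected sample size under the null. The design is right for its stated inputs.

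**Step 2: recompute the weighted average.**

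- Planned mix: (2/3)(10%) + (1/3)(15%) = 6.67% + 5.00% = 11.67%.
- Clinic counts: (57 × 10% + 29 × 15%)/86 = (5.70 + 4.35)/86 = 11.69%.
- Esophagectomy share needed for 13%: (13 − 10)/(15 − 10) = 60%.
- Weights swapped (two thirds esophagectomy): (2/3)(15%) + (1/3)(10%) = 13.3%.

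**Step 3: apply the stated rule at the no-effect rate of the planned patients.** At p = 11.67% the terms of the sum are:

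| Stage 1 leaks x | P(X1 = x) | P(X2 ≤ 7 − x) | Product |
|---|---|---|---|
| 0 | 0.0048 | 0.8781 | 0.0042 |
| 1 | 0.0274 | 0.7692 | 0.0211 |
| 2 | 0.0760 | 0.6131 | 0.0466 |
| 3 | 0.1371 | 0.4265 | 0.0585 |
| 4 | 0.1811 | 0.2453 | 0.0444 |
| Sum | | | 0.1748 |

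The pass probability is 17.5%, or 0.1748/0.0989 = 1.77 times its value at 13%. Modelling 57 patients at 10% and 29 at 15% as separate groups, spread evenly over the two stages, gives 17.2% to 17.3%. The probability of stopping at stage 1, P(X1 ≥ 5), falls from 0.673 at 13% to 0.574 at 11.67%.

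**Step 4: sensitivity to the approximate rates, at the planned mix.**

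| Gastrectomy / esophagectomy rate | Average | P(pass), no effect |
|---|---|---|
| 9.5% / 14.5% | 11.2% | 21% |
| 10% / 15% | 11.7% | 17.5% |
| 10.5% / 15.5% | 12.2% | 14.2% |
| 11% / 16% | 12.7% | 11.5% |

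To average 13% at this mix, gastrectomy would have to be at 12% (with esophagectomy at 15%) or esophagectomy at 19% (with gastrectomy at 10%).

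**Step 5: sensitivity to the mix.** Eligibility (Section 6.2) sets no quota by procedure. If esophagectomy made up 20% of patients the average would be 11% and the pass probability 22.6%. With gastrectomies only, it would be 10% and 32.1%. These are illustrations; the plan expects one third esophagectomy.

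**Step 6: options once p0 = 11.67%, with p1 = 5%.**

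| Rule | Type I error | Power |
|---|---|---|
| 4/43, 7/86 (as planned) | 17.5% | 90.1% |
| 4/43, 6/86 | 10.6% | 84.4% |
| 6/56, 8/109 (smallest N found) | 9.7% | 90.0% |
| 4/41, 9/117 (smallest expected N found) | 10.0% | 90.0% |

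The search for the last two rows covered N from 95 to 129, n1 of at least 20 and a stage 1 limit of at least 1.

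**The case against.** The strongest reply is that the 10% is not miscalculated. It is defined at 13%, which the plan declares unacceptable, and it is correct there. The weights may come from the historical series rather than the planned one. But the documents do not say so, and it would not help: if the device does nothing, the expected leak rate is that of the patients enrolled.

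The second reply is about precision. The component rates are given as approximate and, according to Sections 1.0 and 3.2, rest on verbal communication about institutional databases. This stands as a limit on the figure of 17%, and it works in both directions. It does not recover 13%, because the shift required is larger than rounding.

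Third, the trial counts radiographic as well as clinical leaks and gives every patient a swallow study, while the documents do not say how historical leaks were found. If those were mainly clinical, the no-effect rate under trial ascertainment would be above 11.7%. In addition, 10 of the 86 patients (86 − 76, Section 1.0) come from outside MSK, and no leak rate is given for them. Both are fair caveats: 11.7% is what the plan's own figures imply and is not certain to be the true null.

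Finally, a pass leads only to further investigation, power at 5% is unchanged, and the separate confidence intervals for esophagectomy and total gastrectomy will show part of the case-mix effect. These points soften the consequence but do not change the pooled rule or its stated error rate.

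**Conclusion.** The concern holds. The 13% does not follow from the rates and mix stated beside it, and nothing elsewhere in the document supplies weights that would produce it. On the plan's own figures the no-effect rate is 11.7% and the type I error of the primary rule is about 17%, not 10%. This takes the 10% and 15% rates at face value, the mix as two thirds to one third, and historical leaks as ascertained in the same way as trial leaks. Moving both rates by half a percentage point gives about 14% to 21%. The two-stage calculation itself is correct; only the null rate fed into it is wrong. Because that rate is the trial's sole comparator, it must be corrected before the 10% claim can stand.

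**What to change.** In Section 14.0, replace 13% with the case-mix average of 11.7%, show the weights, and restate the operating characteristics. The sponsor then has an open choice:

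1. Keep 4/43 and 7/86 and state a type I error of about 17% with 90% power at 5%.
2. Keep 86 patients and lower the final cut-off to 6 or fewer leaks: type I error 10.6%, power 84.4%.
3. Keep both errors within 10% and enlarge the trial to about 109 to 117 patients.

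Options 1 and 2 need only changes to the text of Section 14.0 and no added patients or procedures, but each gives up part of the stated 10%/10%. Option 3 keeps it at the cost of 23 to 31 more patients (109 − 86 and 117 − 86). If the sponsor means to retain 13%, the plan must give its weights and explain why that is the no-effect rate for a population that is two thirds gastrectomy.

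A useful addition is to pre-specify that the final null follows the mix actually enrolled, p0 = (10% × gastrectomies + 15% × esophagectomies)/86, with a table of cut-offs by mix. That table would have to be worked out, including how the stage 1 limit is handled. The correction above does not depend on it.

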We plan to accrue 86 patients 76 of which will be accrued at MSK. We expect that accrual will last about 20 months. With follow up of 90 days (+/- 14 days) to evaluate for stricture, we expect the total study time will be 24 months.

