4.1 OVERVIEW OF STUDY DESIGN/INTERVENTION

4.2 Design

Eligible patients at MSKCC and participating sites who are candidates for curative resection of esophageal or gastric cancer (requiring total gastrectomy (TG), proximal gastrectomy (PG) or esophagectomy) will be consented pre-operatively. Patients will undergo standard resection and gastrointestinal anastomosis and will then have reinforcement of the anastomosis with Gentrix PSM. Patients undergoing esophagectomy, PG or TG will be evaluated with one routine postoperative contrast swallow study at post-operative day #4-10.

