17.1 PROTECTION OF HUMAN SUBJECTS

Participation in this trial is voluntary. All patients will be required to sign a statement of informed consent, which will conform to MSKCC IRB guidelines.

1. Risks to the Subjects

Human Subjects Involvement and Characteristics: All patients at MSKCC who meet the inclusion criteria will be eligible. 86 patients will be entered on the trial; patients will be 18 years of age or older. Both men and women and members of all ethnic groups are eligible for this trial. This protocol does not include children because the number of otherwise eligible children is expected to be low. This statement is based on exclusion 4b of the NIH Policy and Guidelines on the Inclusion of Children as Participants in Research Involving Human Subjects.

2. Adequacy of protection against risks

Consent process:

All patients at MSKCC and participating sites who meet the inclusion criteria will be eligible. Participation in the trial is voluntary. All patients will be required to sign a statement of informed consent, which must conform to institutional IRB guidelines. Per MSKCC Policy, an IRB approved Consenting Professional listed on the face page of this trial will conduct the consent discussion with the patient and obtain written informed consent. The informed consent procedure is described in Section 18.

Possible Toxicities/Adverse Effects:

There are no known additional risks of Gentrix devices as described in Section 11.0.

Costs:

Gentrix PSM will be provided to Memorial Sloan-Kettering by ACell. Patients will not receive any compensation for participation in the study. In addition, subjects will not incur any additional costs as a result of participation in the study.

Alternatives:

The alternative to this trial is to have surgery without use of the Gentrix PSM, or have no surgery.

Confidentiality:

Every effort will be made to maintain patient confidentiality. Research and hospital records are confidential. Patients' names and any other identifying information will not be used in reports or publications resulting from this study. Other authorized agencies and appropriate personnel (e.g. qualified monitors from MSKCC) may review patient records as required.

Patient safety:

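### Do the fixed leak limits for 43 and 86 patients fail because Section 14 defines no evaluable set or replacement rule?

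*Combined protocol and SAP*

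**What the plan says.** Section 14.0 takes 13% as the unacceptable leak rate and 5% as the target, with type I and type II error of 10% each. Stage 1 enrols 43 patients. Five leaks end the study; otherwise, "if only 4 or less patients experience a leak then we will proceed to accruing up to 86 patients". Seven or fewer leaks at the end count as success. Exact confidence intervals are planned for the leak rate in all patients, with no further definition of that set.

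Elsewhere 86 is an entry number. Section 1.0 says "We plan to accrue 86 patients 76 of which will be accrued at MSK" and Section 17.1 says "86 patients will be entered on the trial". Neither allows for losses.

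The protocol describes several ways in which a consented patient may yield no leak result:

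- Under Section 4.2 patients "will be consented pre-operatively", yet Section 6.3 excludes "Intraoperative evidence of metastatic or locally-unresectable disease", which is known only at operation.
- Section 9.2 adds: "Patients found to have metastatic disease would not undergo resection and would not be eligible for the study".
- Section 13.0 says that "there are no criteria to remove patients from the trial other than patient withdrawal of consent or death", and that patients who withdraw "will not undergo further trial investigations if they do so".
- Section 10.1 asks for an autopsy when a patient dies within 120 days with no leak on record, but does not say how to count the patient if none is done.

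**The concern.** The limits of 4 and 7 are counts, not rates. If a patient cannot show a leak and is not replaced, fewer patients are at risk while the limits stay put, so a device with a 13% leak rate passes more easily. Dropping the patient and keeping the patient as a non-leak have the same effect on the decision. The design has little room for this, because its exact type I error is just under 10%. Counting such a patient as a leak errs the other way and costs power.

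Two analysts could also report different denominators for the same trial. In an unblinded single-arm study that choice could be made with the outcomes in view. Sections 6.3 and 9.2 can also seem to clash with Section 13.0 over patients found unresectable at surgery.

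**Working it through.** **Inputs (Section 14.0).** Null rate 13%, target 5%, n1 = n2 = 43, continue at 4 or fewer leaks, success at 7 or fewer in total. Stopping at 5 is read as 5 or more, the complement of the rule for continuing.

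**Formula.** P(success | p) = Σ over x = 0..4 of P(X1 = x) · P(X2 ≤ 7 − x), with X1 ~ Bin(n1, p) and X2 ~ Bin(n2, p).

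**The plan's own figures.** With 43 + 43, P(success | 0.13) = 0.0989 and P(success | 0.05) = 0.9012. The stated 10% and 90% are reproduced. The slack in type I error is 0.1000 − 0.0989 = 0.0011.

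**Patients lost and not replaced, limits kept at 4 and 7.** The documents give no loss rate, so the number lost is an assumption.

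| Lost | Type I error at 13% | Power at 5% |
|---|---|---|
| 0 | 0.0989 | 0.901 |
| 1, in stage 2 (43 + 42) | 0.1049 | 0.904 |
| 1, in stage 1 (42 + 43) | 0.1065 | 0.907 |
| 2 | 0.1111-0.1145 | 0.907-0.913 |
| 4 | 0.1242-0.1321 | 0.911-0.924 |

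The first lost patient adds 0.1049 − 0.0989 = 0.0060 or 0.1065 − 0.0989 = 0.0076.

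**One patient counted as a leak instead.** In stage 1 the other patients (42 + 43) face limits of 3 and 6: type I error 0.048, power 0.788. In stage 2 the others (43 + 42) face limits of 4 and 6: type I error 0.059, power 0.849. So the direction of the effect depends on the handling.

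**Who the 43 and 86 are.** The sections, side by side:

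- Section 12.0 defines the primary outcome as the leak rate once the anastomosis has been reinforced with the device. A patient with no anastomosis and no device cannot contribute to it.
- Section 5.4 says that every subject has one device implanted.
- Section 14.0 expects two thirds of the accrued patients to have total gastrectomy and the rest esophagectomy, so accrued patients are patients who were resected.
- Sections 6.3 and 9.2 make a patient with metastatic disease at operation ineligible, and Section 6.3 does the same for locally unresectable disease.
- Section 15.2 requires eligibility to be confirmed at registration. Consent before surgery (Section 4.2) is therefore not the same as accrual.

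Together these make 43 and 86 counts of eligible, implanted patients. Accrual then simply continues past a patient found unresectable, which is replacement in effect, and the first row of the table applies. Section 13.0 governs removal of patients already on the trial. An ineligible patient needs no removal criterion, so it does not conflict with Sections 6.3 and 9.2.

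**What is left.** Only implanted patients with unsettled leak status. Section 10.1 places the swallow at day 4-10 and continues clinical assessment through the hospital stay to about day 90. A missed swallow alone leaves the clinical assessment, and a withdrawal after the swallow leaves a radiographic result. The open cases are withdrawal before either assessment is informative, and death with no documented leak and no autopsy.

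**The case for a change.** The strongest case for a change is that the wording really is silent and a remedy would be cheap. Section 14.0 speaks of enrolling and accruing, no section mentions replacement, and the timing of registration relative to surgery is not given. If patients are registered before the operation and each registration uses one of the 86 places, patients found unresectable would shrink the number at risk. For one unreplaced patient, each way of counting then misses a stated target: dropped or leak-free gives type I error of 0.105-0.107, and counted as a leak gives power of 0.788-0.849. Two sentences would settle it without touching the limits.

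The arithmetic stands, and so does the silence on undetermined status. The premise about patients excluded at surgery does not hold up well, because the outcome definition, the device statement and the description of accrued patients all point to implanted patients. Without that group, nothing in the documents suggests that the number lost would reach 4, where the effect becomes noticeable. The breach of 10% also holds only when the patient is dropped or counted as leak-free, and the plan prescribes neither.

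**Conclusion.** The concern does not call for a change. Read as a whole, the protocol counts eligible patients who received the device, and on that reading the design delivers what it states: type I error 0.0989 and power 0.901.

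The remaining gap is an unwritten convention for a small group. One such patient, dropped or counted as leak-free, would take type I error to 0.105-0.107, which is 0.5 to 0.7 percentage points above a limit quoted as a round 10%. Power would rise slightly. For a single-arm screen whose positive result only supports further investigation, that hardly alters the interpretation. A competent analyst would state the denominator, list any patient with undetermined leak status and show whether the decision depends on how that patient is counted.

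This rests on two assumptions: that registrations found ineligible at surgery do not use up places, and that undetermined leak status among implanted patients is rare. The documents support the first by implication and give no figure for the second.
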